## Protocol Summary

This document represents the protocol summary for the study on human patients. The study will be carried out in accordance with ICH GCP, Helsinki Declaration of World Medical Association, Rules of good clinical practice, approved by order of the Ministry of Health of the Russian Federation dated April 1, 2016 N 200n, , relevant requirements of the regulatory authorities as well as the study procedures.

## Title of Study

Multicenter double-blind placebo-controlled parallel group randomized clinical trial of efficacy and safety of Raphamin in the treatment of coronavirus disease 2019 in outpatient subjects.

**Phase:** III

**Sponsor:** OOO «NPF "MATERIA MEDICA HOLDING», Moscow, Russia

**Protocol No.** MMH-407-006

## Objective of the study

- To evaluate the efficacy and safety of Raphamin in the treatment of Coronavirus Disease 2019 in outpatient subjects.

## Endpoints

### Primary endpoint

1. Frequency of progression of COVID-19 to a more severe level by observation day 28.

### Secondary endpoints

1. Time to sustained clinical recovery from the new coronavirus infection COVID-19.
2. Proportion of patients hospitalized during 28 days of follow-up.

### Additional endpoints

1. Time to COVID-19 progression to more severe level within 28-day follow-up period.

---

 **Severity of COVID-19** will be assessed in accordance with the criteria presented in the current 14th version dated 27.12.2021 Temporary Guidelines on Prevention, Diagnosis and Treatment of New Coronavirus Disease (COVID-19) (COVID-19)” of the Ministry of Health of the Russian Federation:

**Mild:** temperature < 38.0°C, cough, chest congestion, sore throat, nasal congestion/moderate rhinorrhea, cough, weakness, headache, muscle pain, nausea, vomiting, diarrhea, taste loss and olfaction loss, lack of laboured breathing/lack of dyspnea, SpO2≥95%, lack of criteria of moderate or severe form of the disease.

**Moderate:** body temperature >38.0°C; breathing rate >22/min; shortness of breath during exercise; CT (X-ray) changes, typical for viral lesions; SpO2 <95%; serum CRP >10 mg/L.

**Severe:** HR >30/min; SpO2 ≤93%; PaO2 /FiO2 ≤300 mm Hg; reduced consciousness; agitation; unstable hemodynamics (systolic BP < 90 mm Hg or diastolic BP < 60 mm Hg, diuresis < 20 mL/hour); lung changes on CT (X-ray), typical for viral changes; arterial blood lactate >2 mmol/L; qSOFA >2.

 **Stable clinical recovery** is determined as the first day of stable clinical improvement (at least 4 consecutive days, the improvement day is the first of the 4) to grade 1 or 0 (for rhinitis/nasal congestion, sore throat, weakness/fatigue, muscle pain/body ache, headache, chill, fever, nausea, diarrhea), to grade 0 (for dyspnea/laboured breathing and vomiting) to grade ≤ 2 (for cough) and lack of new symptoms grade 1 using 4-point scale (“Assessment of 14 Common COVID-19 Related Symptoms”, Appendix 1); in this case, the axillary temperature should be ≤37.3°C.

2. Proportions of patients with negative PCR test for SARS-CoV-2 on days 6 and 10 of observation.

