During the study, six visits are planned: on days 1, 3, 6, 10, 21, and 28 (visits 1, 2, 3, 4, 5, and 6). Visits 1, 3, and 4 are in person (visits to the patient or visits to the medical center) when the physician examines the patient and monitors EPD records. At visit 3, the patient's adherence to treatment is assessed and laboratory tests are performed. Visits 2, 5 and 6 are phone surveys to determine the patient's condition, presence/absence of complaints. In case of worsening of disease duration, the physician makes an extra visit. Patients with COVID-19 progression to more severe level as well as hospitalized patients are considered as reaching the study endpoints and terminate participation in the study ahead of schedule. The therapeutic approach is determined by the current edition of the clinical recommendations of the Ministry of Health of the Russian Federation «Prevention, diagnosis and treatment of a new coronavirus infection (COVID-19)».

During the study, the use of paracetamol and medicines for the treatment of concomitant diseases is allowed, with the exception of the drugs specified in the section «Prohibited concomitant treatment».

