### ***Symptomatic (Standard) treatment***

Throughout the study the patients may receive an antipyretic medication Paracetamol (provided by the sponsor) and other symptomatic medications (vasoconstrictive nasal agents, antitussive agents).

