### ***Dosage regimens***

Paracetamol (at body temperature  $\geq 38.0$  °C)

Orally, with plenty of liquid, 1-2 hours after eating.

Single dose is 500 (1 tablet). The maximum single dose is 1 g (2 tablets). The maximum daily dose is 4 g (8 tablets). The interval between doses is at least 4 hours. The patient should record thermometry values in EPD before taking the antipyretic drug, its name and dose.

[figure not shown]

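### The recovery definition lets antipyretic days count towards the 4-day window and does not say which temperature reading must be at or below 37.3°C

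*Combined protocol and SAP*

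**What the plan says.** The endpoint is "Time to sustained clinical recovery", listed first under Secondary endpoints. Footnote 2 dates recovery to the start of a run of improvement lasting "at least 4 consecutive days, the improvement day is the first of the 4". On those days:

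- most listed symptoms must be at grade 0 or 1;
- dyspnea and vomiting must be at grade 0;
- cough may be as high as grade 2;
- for temperature, "in this case, the axillary temperature should be ≤37.3°C".

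Medication is not mentioned.

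The permissions are in three places. Study design: "During the study, the use of paracetamol and medicines for the treatment of concomitant diseases is allowed", subject to the prohibited list. Symptomatic (Standard) treatment: "Throughout the study the patients may receive an antipyretic medication Paracetamol", together with nasal vasoconstrictors and antitussives. Neither place attaches a temperature condition. Dosage regimens then heads the paracetamol entry with a body temperature of at least 38.0°C and adds: "The patient should record thermometry values in EPD before taking the antipyretic drug, its name and dose".

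On data capture, Study design has the electronic diary hold timed temperatures twice a day, the 14 symptom scores and antipyretic intake. The Schedule of study procedures marks concomitant therapy at every visit. Nothing under Statistical Analyses uses either record for the recovery endpoint.

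**The concern.** Antipyretics act directly on items in the recovery rule: fever, chill, headache and muscle pain. Most of these pass at grade 1, and patients enter with at least two symptoms at grade 2 or higher (smell and taste may be 1), so a fall of one grade can take an item across the line. A day on which paracetamol does this counts the same as a drug-free day.

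The date of recovery then depends partly on antipyretic use. If use near recovery differs between arms, the between-arm comparison mixes the effect of Raphamin with that of paracetamol. Because the temperature reading that counts is also left open, two analysts could derive different recovery dates from the same diary.

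**Working it through.** **1. The plan's own figure.** The only sizing figure is for the primary endpoint. With a placebo rate of 0.15 and an odds ratio of 0.5, the odds are 0.5 × 0.15/0.85 = 0.0882, so the Raphamin rate is 0.0882/1.0882 = 0.0811. The likelihood-ratio chi-square test at two-sided alpha 0.04 and 80% power needs 356 per group, 712 in total, as stated (power 0.800). Then 712/0.85 = 838. None of this uses the recovery definition. The documents give no hazard ratio, median or sample size for recovery.

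**2. Which days can count.** Taking the passages together:

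| Day | Result under footnote 2 |
|---|---|
| Paracetamol at ≥38.0°C, pre-dose reading counts | Fails 37.3°C, so the day does not count |
| Paracetamol at ≥38.0°C, only the two scheduled readings count | Can pass if both scheduled readings are ≤37.3°C |
| Paracetamol for headache or aches without fever | Temperature passes; symptom is scored at its treated grade |
| Nasal vasoconstrictor, congestion reduced from 2 to 1 | Item passes |
| Antitussive, cough reduced from 2 to 1 | No change, because grade 2 already passes; only 3 to 2 matters |

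In every row the day counts only if all other items also meet their limits.

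**3. Shift in days (all inputs assumed).** Let d be the number of days by which medication brings the scored date forward in users, and g the use near recovery on placebo minus that on Raphamin. The difference between arms in mean recovery time shrinks by d × g:

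- low end: 1 × 0.05 = 0.05 day;
- middle: 2 × (0.30 − 0.20) = 0.2 day;
- high end: 3 × 0.20 = 0.6 day.

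A negative g enlarges the difference by the same amount. Here d is an average over all users. A user for whom the masked item is not the last to resolve contributes zero, which pulls d down.

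**4. Effect on the hazard ratio (all inputs assumed).** Take a true recovery hazard ratio of 1.30, placebo median 8 days, exponential times, censoring at day 28, 712 patients and two-sided alpha 0.05. Let u be the proportion of users and k the factor by which scored recovery is speeded in them. Approximately,

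observed HR ≈ 1.30 × [1 + u(Raphamin)(k − 1)] / [1 + u(placebo)(k − 1)].

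With about 676 recoveries, √(676/4) = 13, so power ≈ Φ(13 × ln HR − 1.96). With no use, 13 × 0.262 − 1.96 = 1.45, giving power 0.93. Worked example for 50% against 40% and k = 1.25: 1.30 × 1.100/1.125 = 1.27.

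| Use, placebo / Raphamin | HR, k = 1.25 | Power | HR, k = 1.5 | Power |
|---|---|---|---|---|
| 50% / 50% | 1.30 | 0.93 | 1.30 | 0.93 |
| 50% / 40% | 1.27 | 0.88 | 1.25 | 0.82 |
| 50% / 30% | 1.24 | 0.80 | 1.20 | 0.64 |
| 60% / 30% | 1.22 | 0.72 | 1.15 | 0.44 |
| 30% / 50% | 1.36 | 0.98 | 1.41 | 0.99 |

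A simulation of the same model with 40,000 patients per arm agrees within about 0.03 on the hazard ratio and about 0.05 on power. Equal use costs almost nothing, more use on placebo dilutes the effect, and more use on Raphamin exaggerates it.

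**The case against.** The strongest reply is that the quoted temperature limb is the best protected part of the definition. Paracetamol taken as Dosage regimens describes follows a recorded reading of at least 38.0°C, and if that reading counts the day already fails. A reading above 38.0°C is also listed among the criteria for moderate disease, and progression ends participation. This stands as far as it goes. It does not cover paracetamol taken for aches or headache, and it depends on a rule about readings that the footnote does not state.

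The three paracetamol passages can be read as a general permission followed by a specific condition. That is fair. They call for clarification and are not a proven contradiction.

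Scoring recovery regardless of permitted symptomatic treatment, alike in two blinded arms, is a legitimate treatment-policy choice. That also stands, but the plan does not state the choice or pair it with a sensitivity analysis. The document describes itself as a protocol summary, so a derivation rule may exist elsewhere.

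Appendix 1 suggests asking for the worst severity in the past 24 hours. This limits masking when a drug wears off between doses. It does not remove it under regular dosing, and it is offered as sample wording.

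A reader might infer that anyone using a decongestant or antitussive daily will be scored as recovered. The documents do not support that: all items must qualify together, and moderate cough passes without treatment. Nor do they show that a drug-free rule could be derived day by day for these agents. The Schedule marks concomitant therapy by visit without mentioning start or stop dates, and among medicines Study design names only antipyretics as a diary entry.

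**Conclusion.** The point holds for antipyretics and for the unspecified temperature reading. Footnote 2 lets a day count as recovered on treated fever, aches or headache, and no analysis rule deals with it.

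A reader might go further and conclude that the endpoint understates the benefit of Raphamin. The documents do not establish a direction. Understatement needs more use on placebo near recovery. A drug that only shortens illness need not produce that, because patients near recovery are at a similar symptom state in both arms. Bias can go either way.

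The size is unknown because no usage rates are given. The 0.05 to 0.6 day range and the hazard ratios above rest wholly on assumed inputs, and the composite nature of recovery makes the upper ends less likely. At equal use the effect is negligible. The endpoint is secondary, and the primary endpoint and sample size do not depend on it. This is a low-cost improvement and does not make the endpoint invalid.

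**What to change.** Add to footnote 2: a day counts towards the 4 consecutive days only if the diary shows no antipyretic taken that day and every temperature recorded that day, including pre-dose readings, is at most 37.3°C. Report the present definition as a sensitivity analysis, and settle both rules before unblinding.

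For nasal vasoconstrictors and antitussives, leave the main definition as it is. Add a supportive analysis that excludes days of use, provided the sponsor confirms that the concomitant therapy record holds day-level dates.

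Study design, Symptomatic (Standard) treatment and Dosage regimens should be reconciled on whether paracetamol use is tied to a temperature reading. Which rule applies is for the sponsor to settle, and nothing here changes what patients may take.

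The cost is one sentence and a derivation from diary data already planned. Recovery times become slightly longer in both arms, and a patient taking an antipyretic for an unrelated reason is dated as recovered later.

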### **Safety assessment**

1. Adverse events (AEs) during the therapy, AEs severity and relation to the study drug, and AEs outcomes.
2. Changes in vital signs during the treatment.
3. Percentage of patients with clinically relevant laboratory abnormalities.

### **Study design**

Study design: multicenter, double blind, placebo-controlled, parallel group randomized clinical trial.

The study enrolls outpatients of either gender aged 18-75 years with increased body temperature  $> 37.5^{\circ}\text{C}$  and other symptoms of upper respiratory infection (cough, chest congestion, sore throat, nasal congestion/moderate rhinorrhea). The investigator should specify the patient's status of vaccination for COVID-19, influenza and other infections. Patients within the first four weeks after any vaccination/booster vaccination are not considered as candidates to participate in the study.

Nasopharyngeal swabs and rapid COVID-19 test are made after signing informed consent (two versions are used: 1) for patients consented for laboratory tests; 2) for patients without the consent). Patients with a positive rapid test and presence of mild COVID-19 (symptoms of upper respiratory infection, no symptoms of moderate or severe levels) within 24 hours after manifestation of the first symptoms of disease are considered as candidates for the study. Oxygen saturation (SpO2) is measured by pulse oximetry in all patients (pulse oximeters are provided by the study sponsor). If SpO2 is  $\geq 95\%$ , a patient may be selected for the study. Baseline severity of COVID-19 symptoms is evaluated using the scoring system «Assessing of 14 Common COVID-19-Related Symptoms» (FDA, 2020). This scoring system assesses the follows symptoms:

1. Stuffy or runny nose.
2. Sore throat.
3. Shortness of breath (difficulty breathing).
4. Cough.
5. Low energy or tiredness.
6. Muscle or body aches.
7. Headache.
8. Chills or shivering.
9. Feeling hot or feverish.

10. Nausea (feeling like you wanted to throw up).
11. Vomiting.
12. Diarrhea.
13. Sense of smell.
14. Sense of taste.

Each symptom is scored individually using the following scoring values:

- Items 1–10: None = 0; Mild = 1; Moderate = 2; and Severe = 3;
- Items 11 and 12: Not at all = 0; 1–2 times = 1; 3–4 times = 2; 5 or more times = 3;
- Items 13 and 14: Sense of smell/taste same as usual = 0; Sense of smell/taste less than usual = 1; No sense of smell/taste = 2.

The minimal baseline score for COVID-19-related symptoms is defined as follows: at least two symptoms with a score of 2 or higher, with the exception of taste and smell where subjects may have a score of 1 or higher, and the absence of shortness of breath (difficulty breathing).

If more severe symptoms are presented, the patient is not included in the study. The therapeutic approach is determined by the current edition of the clinical recommendations of the Ministry of Health of the Russian Federation «Prevention, diagnosis and treatment of a new coronavirus infection (COVID-19)».

At visit 1 (Day 1), in addition to rapid COVID-19 test and SpO2 measurement, the investigator collects complaints and medical history of the patient, performs objective examination including vital signs (blood pressure, heart rate and breathing rate), records concomitant diseases and concomitant therapy, performs nasopharyngeal swabs for PCR (for detection SARS-CoV-2), laboratory tests (if the patient gave his/her consent for blood and urine sampling).

Patients who meet all the inclusion criteria and do not have exclusion criteria at Visit 1 (Day 1) are randomized into one of two groups: patients in group 1 receive Raphamin for 5 days; patients in group 2 receive placebo according to the Raphamin regimen.

If positive PCR test is received (confirmation of new coronavirus disease COVID-19), the patient continues to participate in the study. If PCR result is negative, the patient completes participation in the study ahead of schedule, and his further therapy is determined by the investigator in accordance with the standards of care.

Electronic patient diary (EPD) is utilized in the study, in which morning and evening axillary temperature records are made with the time of measurement. The sponsor provides a classical mercury-free thermometer to each patient. In addition, presence and severity of the disease symptoms according to the scoring system «Assessment of 14 Common COVID-19-Related Symptoms», antipyretics administration and probable worsening of disease duration should also be recorded in EPD. All patients are provided with paracetamol. The physician instructs the patient

how to fill in the diary. The EPD is available for filling in within 28 days of participation in the study.

Overall, patients are observed for 28 days (screening and randomization up to 1 day, treatment for 5 days, follow-up till 28th day).

During the study, six visits are planned: on days 1, 3, 6, 10, 21, and 28 (visits 1, 2, 3, 4, 5, and 6). Visits 1, 3, and 4 are in person (visits to the patient or visits to the medical center) when the physician examines the patient and monitors EPD records. At visit 3, the patient's adherence to treatment is assessed and laboratory tests are performed. Visits 2, 5 and 6 are phone surveys to determine the patient's condition, presence/absence of complaints. In case of worsening of disease duration, the physician makes an extra visit. Patients with COVID-19 progression to more severe level as well as hospitalized patients are considered as reaching the study endpoints and terminate participation in the study ahead of schedule. The therapeutic approach is determined by the current edition of the clinical recommendations of the Ministry of Health of the Russian Federation «Prevention, diagnosis and treatment of a new coronavirus infection (COVID-19)».

During the study, the use of paracetamol and medicines for the treatment of concomitant diseases is allowed, with the exception of the drugs specified in the section «Prohibited concomitant treatment».

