### **Criteria for Withdrawal or Termination**

1. Screening failure.
2. Negative PCR test for SARS-CoV-2.
3. Failure or refusal of the patient to follow the protocol.
4. Deviation from personal visit schedule by more than 1 day.
5. The necessity to use medications not permitted in the study.
6. An adverse event requiring discontinuation of the study drug.
7. Patient's decision to withdraw early for lack of efficacy or other reasons.
8. Pregnancy.

9. Cases not stipulated in the protocol where the investigator decides that further participation may harm the patient.
10. Eligibility error.
11. Participation in any other clinical study.
12. Unblinding.

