### **Number of patients**

It is planned to include 838 patients, 798 of them will be randomized which is expected to yield at least 712 patients (356 per Raphamin and Placebo groups) completing all the protocol procedures.

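### Participation ends at progression or admission, so later admissions have no route into the 28-day hospitalisation endpoint and later recovery is unobserved

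*Combined protocol and SAP*

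**What the plan says.** - **Exit rule (Study design, paragraph on visits).** Patients who progress, and patients who are hospitalised, "are considered as reaching the study endpoints and terminate participation in the study ahead of schedule".
- **Primary endpoint.** "Frequency of progression of COVID-19 to a more severe level by observation day 28".
- **Secondary endpoints.** "Time to sustained clinical recovery", and "Proportion of patients hospitalized during 28 days of follow-up". Footnote 2 requires improvement to hold for "at least 4 consecutive days, the improvement day is the first of the 4", with a temperature condition.
- **Follow-up tools (Study design).** "The EPD is available for filling in within 28 days of participation in the study". Visits 5 and 6 (Days 21 and 28) are phone surveys.
- **Schedule of study procedures.** An unscheduled visit for aggravation records symptoms, SpO2 and diary, and study completion may take place there. Nothing is listed after early completion. The 14-symptom evaluation is not ticked for the phone visits.
- **Criteria for Withdrawal or Termination, item 5.** "The necessity to use medications not permitted in the study" is a further reason to end participation.
- **Samples.** Progression is not among the Full Analysis Set exclusions. The per-protocol (PP) set requires all scheduled visits. Footnote 4, under Evaluation of sample size, admits patients whose primary endpoint status can still be determined despite some missing data.
- **Non-parametric criteria.** For survival analysis only LIFETEST and PHREG are named. No censoring or competing-event rule appears.

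**The concern.** Patients enter with mild disease, and the next level is moderate. Footnote 1 lists temperature above 38.0°C and CRP above 10 mg/L among the moderate criteria, so a patient can be classed as progressed while still at home. If that patient is admitted later, participation has already ended and no procedure is described for recording the admission. The patients who leave are plausibly those at higher risk of admission.

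Recovery has the same gap. Progressors stay in the Full Analysis Set with a truncated symptom record, and the document does not say whether they are censored, kept as not recovered, or given a competing event.

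The loss depends on the primary outcome. If Raphamin works, more placebo than Raphamin patients lose later follow-up. If it does not, the expected loss is equal by arm, but hospitalisation is still undercounted. An analysis rule alone cannot restore observations that were never made.

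**Working it through.** **1. The plan's own sample size.** The sizing code has placebo rate 0.15, OR 0.5, likelihood-ratio chi-square, alpha 0.04 and power 0.80.

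- Raphamin rate: odds = 0.5 × 0.15/0.85 = 0.0882; p = 0.0882/1.0882 = 0.0811.
- Non-central chi-square with 1 df gives 356 per group, 712 in total (power 0.8001), matching the plan.
- 712/(1 − 0.15) = 838, also matching. 838 × 0.95 = 796, against 798 stated.

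The sizing is not affected by this point.

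**2. Expected exits at progression (rate × group size).**

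| Scenario | Placebo | Raphamin | Total |
|---|---|---|---|
| 0.15, OR 0.5, 399 per group | 59.9 | 32.4 | 92.2 of 798 (11.6%) |
| 0.15, OR 0.5, 356 per group | 53.4 | 28.9 | 82.3 of 712 |
| 0.20, OR 0.5 (Raphamin 0.111), 399 per group | 79.8 | 44.3 | 124.1 of 798 (15.6%) |
| 0.15, no effect, 399 per group | 59.9 | 59.9 | 119.7 of 798 |

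The 0.20 row is an assumption, shown because the plan gives 0.15 as a minimum. Each total is an upper bound on secondary data lost from this cause at those rates, because some progressors are admitted at or before the progression visit, or have already met the recovery definition.

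**3. Hospitalisation.** Let h be the share of progressors admitted only after exit. The documents give no value, so h is assumed. Missed proportion = p × h.

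| h (assumed) | Placebo, points | Raphamin, points | Patients, 399 per group |
|---|---|---|---|
| 0.05 | 0.75 | 0.41 | 4.6 |
| 0.10 | 1.5 | 0.81 | 9.2 |
| 0.30 | 4.5 | 2.43 | 27.7 |

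**4. Recovery: does the unstated rule matter?** This is an illustration; every input except the two progression rates is assumed.

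- 399 per arm, with equal exponential recovery in non-progressors (median 5, 7, 10 or 14 days).
- Progression day uniform on Days 2–6 or 2–14; no progressor recovers before progressing.
- Last possible recovery day 25, since four days are needed; administrative censoring at Day 28.
- Eight scenarios, 1,000 replicates each. A hazard ratio (HR) above 1 favours Raphamin.

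| Rule for progressors | Mean log-rank z | HR for recovery |
|---|---|---|
| Censored at progression | 0.2 to 1.1 | 1.02 to 1.09 |
| Kept as not recovered to Day 28 | 1.4 to 2.4 | 1.13 to 1.21 |
| Followed (assumed median 10 days after progression) | 0.0 to 1.4 | 1.00 to 1.11 |

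Repeat runs move the ends of the HR ranges by up to 0.02. In round terms the contrast is 1.13 to 1.22 for the middle rule against 1.00 to 1.13 for the other two. Censoring and full follow-up differ by at most about 0.04 in HR within a scenario.

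A second illustration uses constant, equal recovery hazards with median 5, 7 or 10 days. Censoring at progression gives no Day-28 difference. Treating progression as a competing event gives 84.0% against 90.4%, 81.3% against 87.1%, and 75.2% against 80.1% (placebo against Raphamin), differences of 6.4, 5.8 and 4.9 points. The competing-event result carries the progression effect with it and must be labelled accordingly.

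**5. Per-protocol set.** 798 − 712 = 86 expected non-completers. Under Number of patients, 798 randomised is the number "which is expected to yield at least 712 patients" completing all procedures. Whether progressors count among the 712 is not stated; if they did not, the 92 expected progressors alone would exceed the 86.

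**The case against.** **Exclusion of later admissions is an inference.** No sentence says that an admission after exit is left out, so a reader should not infer a stated rule to exclude it. This stands. The supportable statement is that participation ends and no route for capturing the admission is described.

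**The text calls itself a protocol summary.** Its statistical section is a general list of methods, so a fuller document may hold the recovery rule. That is fair for the missing rule, and one should not infer that the sponsor has none. It is weaker for the missing observation: the exit rule and visit schedule are specific, and general 28-day observation does not override an explicit early exit.

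**The primary endpoint is sound.** A reader might infer that it is compromised. The documents do not support that: progression, and the time to it, are recorded when a patient leaves for that reason. Nor is admission a severity criterion in footnote 1, so a patient admitted without a recorded severity change has, read plainly, reached the hospitalisation endpoint only. What remains is that progression after such an exit is not seen; its size cannot be derived.

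**The per-protocol set.** One might infer that it drops every primary event. Footnote 4 points the other way, so this is a wording conflict to reconcile.

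**The recovery bias is small or hypothetical.** Partly right. Censoring and full follow-up nearly coincide in the illustration, so a claim that censoring would seriously distort recovery is not supported. The only rule there that departs clearly, keeping progressors as not recovered to Day 28, is one that no section proposes.

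**Follow-up after progression mixes in other therapy.** True. Recovery regardless of later care and recovery without prior progression are both legitimate targets; the plan needs to say which it estimates.

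**Conclusion.** The point holds for the two secondary endpoints and should be fixed. Up to about 92 of 798 patients (11.6%), 60 placebo and 32 Raphamin, leave at progression if the planning rates are right. This is a ceiling on the secondary data lost from this cause, not an estimate of it. The hospitalisation undercount has no estimate in the documents; the 5 to 28 patients above rest wholly on an assumed h of 5% to 30%. For recovery, the illustration shows that the rule can matter, not how much it will.

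**What to change.** 1. **Study design.** Record progression or hospitalisation as the event, but continue data collection to Day 28 through the existing diary and the remaining phone visits, covering hospitalisation, vital status and symptoms. Keep the diary open after the event. The phone visits carry no 14-symptom evaluation, so recovery must come from the diary or that evaluation must be added to these patients' calls.
2. **Withdrawal criteria, item 5.** Reconcile it with this follow-up: whatever the plan decides about treatment or participation when non-permitted medication is needed, that need should not end this data collection. No treatment rule changes.
3. **Recovery analysis, stated before unblinding.** Progressors stay at risk until the diary shows recovery, with censoring at Day 28 and death as a competing event (never recovered). If follow-up cannot continue, analyse progression as a competing event and label the result recovery without prior progression.
4. **Samples.** Reconcile the all-visits requirement with footnote 4, so that reaching the endpoint does not by itself exclude a patient from the per-protocol set.

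**Cost.** Wording changes in three sections, one analysis rule, and continued diary entries and calls for about 92 patients at the planning rates. Some diaries will be missing in hospitalised patients, so the recovery gap closes only in part. Data after progression will include non-study therapy, making the recovery comparison a treatment-policy one.
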